### 7.2 Clinical Study Design

This is a prospective, parallel group, multi-center, randomized, observer masked study comparing topography guided LASIK vs. SMILE, both of which are commercially available in the countries where the study is being conducted.

Potential subjects are screened and up to 450 subjects (225 subjects per treatment group) are enrolled at approximately 8 study sites in order to achieve about 185 evaluable subjects per treatment group. In total, 740 eyes from approximately 370 subjects are required for this study.

Subjects (18 years or older [subjects in Singapore must be 21 years of age or older and subjects in Korea must be upon completion of 19 years of age or older due to local regulations]) with myopia requiring refractive error correction of -0.5 to -8.0 D optical infinity adjusted manifest refraction sphere and astigmatism correction of -0.75 to -5.0 D manifest refraction cylinder and at least 0.75 D of corneal astigmatism in both eyes, and fulfilling all other eligibility criteria, are enrolled into the study and undergo pre-surgery screening. Among other exclusion criteria, subjects are excluded if they have a history or evidence of active or inactive corneal disease, and systemic disease and medications that may confound wound healing.

Qualifying subjects are required to attend a total of 7 visits over a period of up to 15 months (See Section 9.1).

Subjects are randomized 1:1 by investigational site during the Pre-Surgery period to undergo bilateral surgery with either Topography Guided LASIK or SMILE scheduled on Day 0.

The main analyses for effectiveness and safety are conducted when the last subject completes the 3 months Post-Surgery follow-up Visit. Subjects are followed-up for an additional 9 months (Day 330 to Day 375) for safety and assessments. Final data analyses are conducted at study completion.

[figure not shown]
An overview of the study design is presented in Figure 7–1.

Alcon - Business Use Only Protocol - Clinical Effective Date: 19-Mar-2017 Page 37 of 81

Document: TDOC-0052425 Version: 2.0; Most-Recent; Effective; CURRENT

Status: Effective

Figure 7–1 Study Design

Site personnel performing the manifest refraction subjective assessment and all uncorrected visual acuity (UCVA) testing after randomization are to remain masked with regard to treatment assignment until after the final database lock (DBL). Alcon and other site personnel [e.g., nurses and technicians involved with the surgery, site personnel entering data in the electronic case report forms (eCRF), site personnel administering other study related procedures, e.g. Refractive Status and Vision Profile (RSVP) and short questionnaire for dry eye syndrome (SQDES) questionnaires] must not reveal the treatment assignment to masked site personnel at any time during the study. Refer to Section 13.5 for unmasking of study information.

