### **Safety Objectives** 8.4

The safety objectives of the study are:

- To evaluate the adverse events (AEs) associated with Topography Guided LASIK and SMILE.
- To evaluate post-surgery BCVA after Topography Guided LASIK and SMILE.
- To evaluate mesopic uncorrected contrast sensitivity after Topography Guided LASIK and SMILE.
- To evaluate quality of vision and vision related quality of life after Topography Guided LASIK and SMILE.

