### 12.1.3 Post-Surgery follow-up Visits (Day 1, Week 1, Months 1, 3 and 12)

Below is a list of study procedures to be undertaken at the Post-Surgery follow-up Visits (Day 1, Week 1 [Day 5 to Day 9], Months 1 [Day 21 to Day 35], 3 [Day 70 to Day 98] and 12

Effective Date: 19-Mar-2017 Page 58 of 81 Alcon - Business Use Only Protocol - Clinical

Version: 2.0; Most-Recent; Effective; CURRENT Document: TDOC-0052425

Status: Effective

[Day 330 to Day 375]). Procedures must be performed in the order presented below unless otherwise stated. All ocular assessments must be done monocularly.

- 1. Record any changes to subjects' ocular and non-ocular medical history or concomitant medications at all visits.
- 2. Administer the RSVP Questionnaire at the Month 1, 3, and 12 visits.
- 3. Administer the SQDES Questionnaire at the Month 1, 3, and 12 visits.

NOTE: Investigators and site staff must review both questionnaires results prior to subjects leaving the office to ensure completeness.

- 4. Conduct the following procedures in an order that is feasible for your site:
  - Perform lighting measurements for VA and contrast sensitivity testing at all visits.
  - Measure distance UCVA in photopic conditions at all visits.
  - Measure uncorrected contrast sensitivity in mesopic conditions at the Month 1, 3, and 12 visits.
  - Measure manifest refraction at 4 meters and adjust for optical infinity at the Week 1, Month 1, 3, and 12 visits.
  - Measure distance BCVA in photopic conditions at the Week 1, Month 1, 3, and 12 visits.
- 5. Conduct the following procedures in an order that is feasible for your site:
  - Perform topography at the Month 1, 3, and 12 visits.

- 6. Perform slit lamp examination at all visits.
- 7. Measure IOP at the Month 1, 3, and 12 visits.
- 8. Perform dilated fundus examination at Month 12.
- 9. Record any AEs at all visits. Refer to Section 13 for further details.

*NOTE*: SAEs must be entered into EDC within 24 hours of the Investigator's knowledge.

*NOTE:* Secondary Surgical Intervention: Retreatments will not be allowed in this study.

Effective Date: 19-Mar-2017 Page 59 of 81 Alcon - Business Use Only Protocol - Clinical

Version: 2.0; Most-Recent; Effective; CURRENT Document: TDOC-0052425

Status: Effective

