## Specific Events Relevant to this Protocol

In addition to reporting all AEs (serious and non-serious) meeting the definitions, the Investigator must report any occurrence of the following ocular events as a serious adverse event (SAE):

- Diffuse lamellar keratitis moderate or worse.
- Corneal infiltrate or ulcer.
- Any persistent corneal epithelial defect at one month or later.
- Moderate or severe (as defined in Section 13.3) corneal edema at 1 month or later (for LASIK, specify flap or bed).
- Melting of the flap (LASIK only).
- Decrease in BCVA of greater than or equal to 2 lines (≥ 10 letters ETDRS).
- Retinal detachment.
- Ocular perforation.

Any other potentially sight-threatening event may also be considered serious based on the judgment of the Investigator and should be reported appropriately.

Alcon - Business Use Only Protocol - Clinical Effective Date: 19-Mar-2017
Page 63 of 81

Document: TDOC-0052425 Version: 2.0; Most-Recent; Effective; CURRENT

Status: Effective

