## 13.5 Unmasking of the Study Information

Site personnel performing the manifest refraction subjective assessment and all UCVA testing after randomization are to remain masked with regard to treatment assignment until after the final DBL. Alcon and other site personnel (nurses and technicians involved with the surgery, site personnel entering data in eCRF, site personnel administering other study related procedures, e.g. RSVP and SQDES questionnaires) must not reveal the treatment assignment to masked site personnel at any time during the study.

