1.4 Masking

This is an observer masked study. This means that site personnel performing the manifest refraction subjective assessment and all UCVA testing after randomization will remain masked with regard to treatment assignment until after the final DBL.

Surgery assignment may be known to Alcon, Novartis, and other site personnel (e.g., nurses and technicians involved with the surgery, staff entering data in the electronic case report form (eCRF), site personnel administering other study related procedures, e.g. Refractive Status and Vision Profile [RSVP] and Short questionnaire for dry eye syndrome [SQDES] questionnaires). However they will not reveal the surgery assignment to masked site personnel at any time during the study.

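### The masking rule covers only the manifest refraction and UCVA testers, so BCVA and mesopic contrast sensitivity, both named safety objectives, may be tested by unmasked staff

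*Protocol*

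**What the plan says.** Masking is described in three places, and all three agree.

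- Protocol 7.2: "Site personnel performing the manifest refraction subjective assessment and all uncorrected visual acuity (UCVA) testing after randomization are to remain masked".
- Protocol 13.5: "Site personnel performing the manifest refraction subjective assessment and all UCVA testing after randomization are to remain masked with regard to treatment assignment".
- SAP 1.4, as the definition of an observer-masked study: "This means that site personnel performing the manifest refraction subjective assessment and all UCVA testing after randomization will remain masked".

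SAP 1.4 then says who may be unmasked: "Surgery assignment may be known to Alcon, Novartis, and other site personnel". The examples include "site personnel administering other study related procedures, e.g. Refractive Status and Vision Profile" and the dry eye questionnaire. They are introduced as examples, so the list is open. Unmasked staff must not disclose the assignment to masked staff.

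The safety objectives in Protocol 8.4 include "To evaluate post-surgery BCVA after Topography Guided LASIK and SMILE" and a parallel objective for mesopic uncorrected contrast sensitivity. Protocol 12.1.3 lists each as a procedure of its own. For BCVA it reads "Measure distance BCVA in photopic conditions at the Week 1, Month 1, 3, and 12 visits"; contrast sensitivity is measured at Months 1, 3 and 12. Neither entry says who performs the test or whether that person is masked. Protocol 13.1 makes "Decrease in BCVA of greater than or equal to 2 lines" a mandatory serious adverse event (SAE), and SAP 6.3.2 tabulates and lists such losses. Protocol 15.7 and SAP 6.2 keep the safety analysis descriptive.

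**The concern.** BCVA and contrast sensitivity depend on the subject's responses and on how far the tester prompts, just as UCVA does. The plan masks the UCVA tester. BCVA is read on the same type of chart at the same permitted distances, yet its tester is left in the group that may know the assignment. No reason is given for treating them differently.

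At stake is the between-arm safety comparison of the sponsor's laser with a competitor's. A tester who knows the assignment could push one arm's readings up or down. That would shift mean BCVA, the line-change table, the contrast sensitivity means and, through the 2-line rule, the SAE count. Descriptive reporting does not protect against this, because readers will still compare the arms.

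**Working it through.** The plan gives no figure on this point, so there is none to reproduce. The check has two parts.

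**1. Coverage of the masking rule**, from Protocol 7.2, 8.4, 12.1.3, 13.5 and Table 6-1, and SAP 1.4.

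| Test | Role | Post-surgery visits | Tester masked? |
|---|---|---|---|
| Manifest refraction | Primary endpoint, first secondary endpoint | Week 1, Months 1, 3, 12 | Yes |
| UCVA | Second secondary endpoint | Day 1, Week 1, Months 1, 3, 12 | Yes |
| BCVA | Safety objective, SAE trigger | Week 1, Months 1, 3, 12 | Not stated |
| Mesopic contrast sensitivity | Safety objective | Months 1, 3, 12 | Not stated |

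Two things follow. The tested hypotheses rest only on the first two rows, so the gap does not reach them. And every scheduled post-surgery visit with BCVA or contrast sensitivity also has manifest refraction and UCVA, so a masked tester must already attend. All four tests sit in step 4 of Protocol 12.1.3, to be done in whatever order suits the site.

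**2. Size of a possible bias in BCVA (illustration).**

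Inputs:
- One ETDRS letter is 0.02 logMAR. Two lines are 10 letters (Protocol 13.1), so one line is 5.
- Assumed: the SD of BCVA change is 0.06, 0.08 or 0.10 logMAR, which is 3, 4 or 5 letters. The documents give no value.
- Assumed: no true mean change, and a bias of one letter of extra loss for every eye in one arm.

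For loss counted in whole letters, with mean shift m letters and SD s letters:

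P(loss of at least k letters) = 1 − Φ((k − 0.5 − m)/s)

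| SD (logMAR) | At least 1 line, no bias | At least 1 line, 1-letter bias | At least 2 lines, no bias | At least 2 lines, 1-letter bias |
|---|---|---|---|---|
| 0.06 | 1−Φ(4.5/3) = 6.7% | 1−Φ(3.5/3) = 12.2% | 1−Φ(9.5/3) = 0.08% | 1−Φ(8.5/3) = 0.23% |
| 0.08 | 1−Φ(4.5/4) = 13.0% | 1−Φ(3.5/4) = 19.1% | 1−Φ(9.5/4) = 0.88% | 1−Φ(8.5/4) = 1.68% |
| 0.10 | 1−Φ(4.5/5) = 18.4% | 1−Φ(3.5/5) = 24.2% | 1−Φ(9.5/5) = 2.87% | 1−Φ(8.5/5) = 4.46% |

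With 370 evaluable eyes per arm (185 subjects, two eyes each; Protocol 15.9), the 2-line column moves from 370 × 0.00077 = 0.3 to 370 × 0.0023 = 0.9 eyes at the lowest SD, and from 370 × 0.0287 = 10.6 to 370 × 0.0446 = 16.5 eyes at the highest.

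The direction is arbitrary. If the tester's encouragement instead gains one letter in one arm (m = −1), the 2-line share falls from 0.08% to 1−Φ(10.5/3) = 0.02% at SD 0.06, and from 2.87% to 1−Φ(10.5/5) = 1.79% at SD 0.10.

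No such calculation was made for contrast sensitivity, because the documents give neither a spread nor a threshold for it.

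**The case against.** The other side has real points.

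- *The same masked person probably measures BCVA.* BCVA is acuity through the manifest refraction and comes after it in the procedure list, so a handover to an unmasked colleague is not the natural reading. This stands as a likelihood and weakens the BCVA half. It is not a requirement, and it does not carry over to contrast sensitivity, which is measured uncorrected and does not depend on the refraction.
- *The Manual of Procedures may assign testers.* It holds the assessment details and was not available. This stands. Even so, the protocol and SAP each state the masking rule, and both leave these tests out.
- *Masking the confirmatory endpoints is proportionate.* Study success rests on cylinder, the two secondary endpoints are cylinder and UCVA, and safety has no hypotheses. This limits the consequence but does not remove it: SAP 6.3.1 itself intends a descriptive comparison of adverse events between arms.
- *The size is assumed.* It is. A uniform one-letter bias across about 8 sites is a strong assumption, and at the lower end the 2-line share hardly moves.
- *If separate staff do the tests, the fix costs more than wording.* Correct. Those sites would have to reassign work.

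A reader might infer that BCVA and contrast sensitivity are in fact tested unmasked. The documents do not support that: they permit it, and nowhere list acuity testers among the staff who know the assignment. A reader might also infer that the superiority claim is compromised. It is not, since the testers for all three tested endpoints are to be masked.

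**Conclusion.** The point holds as a gap in the masking rule. It is certain from the text that neither document requires the BCVA and contrast sensitivity testers to be masked. It is firmest for contrast sensitivity and weaker for BCVA. What is exposed is the descriptive safety comparison, including SAEs triggered by BCVA loss.

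The size of any bias is unknown. The illustrated shift in eyes losing 2 or more lines, from 0.1-2.9% to 0.2-4.5%, depends wholly on the assumed SD, the assumed one-letter bias in one arm, and no true change. It shows what a small bias could do, not what is expected. This is a cheap improvement worth making, not a flaw that threatens the trial's main conclusion.

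**What to change.** In Protocol 7.2, Protocol 13.5 and SAP 1.4, extend the masking sentence so that it covers *manifest refraction, UCVA, BCVA and contrast sensitivity testing after randomization*. Have the masked tester already required at Week 1 and Months 1, 3 and 12 carry out the whole block, and check that the Manual of Procedures says the same.

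The cost is wording and site training. Scheduling becomes tighter, and sites that now split the block must reassign some work. Sample size and analysis do not change. Subject-side bias would remain, because neither document masks subjects.

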## 8 CLINICAL STUDY OBJECTIVES

# 8.1 Primary Objective

The primary objective of the study is to demonstrate that Topography Guided LASIK is superior to SMILE in the percentage of eyes with manifest refraction cylinder  $\leq 0.5$  D at 3 months.

Effective Date: 19-Mar-2017 Page 38 of 81 Alcon - Business Use Only Protocol - Clinical

Version: 2.0; Most-Recent; Effective; CURRENT Document: TDOC-0052425

Status: Effective

#### **Secondary Objectives** 8.2

The secondary objectives of the study are:

- To demonstrate that Topography Guided LASIK is superior to SMILE in mean manifest refraction cylinder at 3 months.
- To demonstrate that Topography Guided LASIK is superior to SMILE in mean UCVA at 3 months.

### **Safety Objectives** 8.4

The safety objectives of the study are:

- To evaluate the adverse events (AEs) associated with Topography Guided LASIK and SMILE.
- To evaluate post-surgery BCVA after Topography Guided LASIK and SMILE.
- To evaluate mesopic uncorrected contrast sensitivity after Topography Guided LASIK and SMILE.
- To evaluate quality of vision and vision related quality of life after Topography Guided LASIK and SMILE.

### 8.5 **Study Endpoints**

### 8.5.1 **Effectiveness Endpoints**

The primary effectiveness endpoint is the percentage of eyes with manifest refraction cylinder  $\leq 0.5$  D at 3 months.

Effective Date: 19-Mar-2017 Page 39 of 81 Alcon - Business Use Only Protocol - Clinical

[figure not shown]
Version: 2.0; Most-Recent; Effective; CURRENT Document: TDOC-0052425

Status: Effective

Secondary effectiveness endpoints are as follows:

Mean manifest refraction cylinder at 3 months.

Mean UCVA at 3 months.

Effective Date: 19-Mar-2017 Page 40 of 81

Document: TDOC-0052425 Version: 2.0; Most-Recent; Effective; CURRENT

Status: Effective

# 8.5.2 Safety Endpoints

The secondary safety endpoints are as follows:

- Frequency of treatment-emergent AEs.
- Mean intraocular pressure (IOP) at Screening, 1 month, 3 months, and 12 months.
- Frequency of device deficiencies
- BCVA:
  - o Mean BCVA at Screening, 1 week, 1 month, 3 months, and 12 months.
  - Percentage of eyes with post-surgery BCVA more than two lines better, two lines better, one line better, less than one line better and greater than one line

Alcon - Business Use Only Protocol - Clinical Effective Date: 19-Mar-2017
Page 41 of 81

Document: TDOC-0052425 Version: 2.0; Most-Recent; Effective; CURRENT

Status: Effective

worse, one line worse, two lines worse, more than two lines worse than pre-surgery BCVA at Screening, 1 week, 1 month, 3 months, and 12 months.

- Uncorrected contrast sensitivity:
  - Mean mesopic uncorrected contrast sensitivity at each contrast level at Screening, 1 month, 3 months, and 12 months.
- Quality of vision and quality of life (for both RSVP and SQDES):
  - RSVP: Mean overall and subscale vision related quality of life score at Screening, 1 month, 3 months, and 12 months.
  - SQDES: Frequency of dry eye syndrome at Screening, 1 month, 3 months, and 12 months.

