# 15.7 Safety Analysis

No inferential testing will be performed on these parameters.

The eye-level safety analyses will be performed using the safety analysis set. For safety parameters collected on the subject-level (e.g. PRO questionnaires, non-ocular AEs), the population of interest will be the set of subjects with at least one eye for which treatment has begun (i.e. at least one eye in the safety analysis set).

Alcon - Business Use Only Protocol - Clinical Effective Date: 19-Mar-2017
Page 73 of 81

Document: TDOC-0052425 Version: 2.0; Most-Recent; Effective; CURRENT

Status: Effective

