### Adverse Events

AEs will be assessed throughout the study period (from pre-surgery Day -45 up to post-surgery follow-up for Month 12). For more details, refer to Section 13.1.

AEs will be deemed treatment emergent if the onset date is on or after the date of surgery. Any AEs recorded prior to the start of surgery will be listed separately from the treatment emergent AEs. Only treatment emergent adverse events (TEAEs) will be summarized. Ocular treatment emergent adverse events will be summarized separately by SOC and PT.

Both subject and event counts will be presented for AEs. Subject counts refer to the number of subjects with the respective AE of interest. Subjects who experience multiple AEs for a PT will be counted once, similarly for subjects with multiple AEs per SOC, for subject counts. Event counts refer to the number of occurrences of the respective AE of interest, regardless of whether a subject already had this event.

All information obtained on AEs (including those which are collected pre-surgery as well as TEAEs) will be displayed by treatment and subject.

Although the surgery is planned to be bilateral, the investigator may decide to not perform the surgery on the second eye on the same day as the first eye. In the following scenarios, if during the 12-month post-surgery study period:

- no surgery is performed on the second eye
- surgery is performed on the second eye using a non-study surgery

Then only AEs will be collected for the second eye.

These AEs (including those which are collected pre-surgery as well as those after the planned surgery) will be listed separately.

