6.1 Safety Endpoints

The safety endpoints are:

- Mean intraocular pressure (IOP) (mmHg) at each study visit
- Mean mesopic uncorrected contrast sensitivity at each contrast level at each study visit
- Mean BCVA (logMAR) at each study visit
- Percentage of eyes with post-surgery BCVA that is ≥ 2 lines better, 1 to < 2 lines better, >0 to < 1 line better, no change, < 0 to < 1 line worse, 1 to < 2 lines worse, ≥ 2 lines worse than pre-surgery BCVA at each study visit
- Frequency of dry eye syndrome at each study visit
- Mean overall and subscale vision related quality of life score at each study visit
- Frequency of AEs

- Frequency of device deficiencies

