6.3.1 Adverse Events

The applicable definition of an AE is in the study protocol. All AEs occurring from when a subject signs the ICF to when a subject exits the study will be accounted for in the reporting. Analysis and presentation of AEs occurring during the 45 day pre-surgery period (the screening period) will be separated from those occurring during the post-surgery period where a comparative evaluation (descriptive only) of treatment-emergent AEs (TEAEs) is intended. A TEAE is an event not present prior to surgery (Topography Guided LASIK, SMILE) or any pre-existing event that worsens following surgery. The period for TEAE analysis starts from when study treatment has begun to 12 months post-surgery (Day 330 to Day 375). Study treatment will be considered to have begun once the flap creation is initiated for Topography Guided LASIK and once the laser touches the eye for SMILE.

Descriptive summaries (subject counts and percentages, event counts) by surgery group for specific AEs will be presented by primary SOC and PT of the Medical Dictionary for Regulatory Activities (MedDRA) dictionary (Version 19.0 or a more recent version). The SOCs will be presented in alphabetical order. PTs will be ordered for each surgery group in decreasing proportion in the Topography Guided LASIK surgery group of interest (study surgery group 1). The following summary tables will be provided:

- Ocular AEs for all eyes in the Safety Analysis Set (TEAE only)
- Ocular SAEs for all eyes in the Safety Analysis Set (TEAE only)
- Adverse device effects (ADEs) for all eyes in the Safety Analysis Set (TEAE only)

- Serious ADEs (SADEs) for all eyes in the Safety Analysis Set (TEAE only)

Both subject and event counts will be presented for AEs. Subject counts refer to the number of subjects with the respective AE of interest. Subjects who experience multiple AEs for a PT will be counted once, similarly for subjects with multiple AEs per SOC, for subject counts. Event counts refer to the number of occurrences of the respective AE of interest, regardless of whether a subject already had this event.

Individual subject's listings will also be provided. These will include:

- Ocular AEs for all eyes in the Safety Analysis Set
- Ocular AEs for all eyes not in the Safety Analysis Set
- Non-ocular AEs for all enrolled subjects
- Listing of deaths for all enrolled subjects

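### The AE safety endpoint covers all treatment-emergent events, but the planned tables give no count by arm for non-ocular events judged unrelated to treatment

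*Protocol*

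**What the plan says.** **Endpoint.** Protocol 8.5.2 lists "Frequency of treatment-emergent AEs" and the synopsis agrees. SAP 6.1 has "Frequency of AEs". The first safety objective in Protocol 8.4 is "To evaluate the adverse events (AEs) associated with Topography Guided LASIK and SMILE". None of these is confined to the eye, and the Protocol glossary (Section 4) defines an AE as covering any untoward medical occurrence.

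**Population.** Protocol 15.7 provides for events that belong to a person and not to an eye: "For safety parameters collected on the subject-level (e.g. PRO questionnaires, non-ocular AEs), the population of interest will be the set of subjects". The sentence goes on to require that treatment began in one eye or both. SAP 6.3 repeats this and also gives non-ocular AEs as an example. SAP 3 states the general rule that subject-level data use a subject-level version of the analysis set.

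**Analysis.** The Adverse Events part of Protocol 15.7 says: "Only treatment emergent adverse events (TEAEs) will be summarized. Ocular treatment emergent adverse events will be summarized separately by SOC and PT". SAP 6.3.1 then names four summary tables. The first is ocular AEs and the second is "Ocular SAEs for all eyes in the Safety Analysis Set (TEAE only"). The third and fourth are ADEs and SADEs, which do not carry the word ocular but are specified over the eyes of the same set. For the remaining events SAP 6.3.1 provides a listing, "Non-ocular AEs for all enrolled subjects", and a listing of deaths.

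**Intent.** The Amendment 1 rationale for Section 15.7 says that non-ocular TEAEs are not to be summarised.

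**The concern.** A frequency endpoint needs a numerator, a denominator and a planned display by arm. Here the stated endpoint takes in every treatment-emergent event, while the displays that would report it are built around the eye. If the plan is followed exactly, the stated frequency is never produced.

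The practical risk is in reading the report. The AE tables would stand under an endpoint label wider than their content, and an unrelated non-ocular hospitalisation or other serious event would enter no total. Whether a non-ocular event could be counted at all would depend on a causality judgement, and the masking in Protocol 7.2 covers only the staff who perform manifest refraction and uncorrected acuity testing. A count that does not depend on attribution is the usual safeguard, and the plan has none for non-ocular events.

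**Working it through.** The plan states no figure for this point, so the check sets the endpoint against the full list of planned AE output.

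1. *Scope of the endpoint.* All TEAEs (Protocol 8.5.2, synopsis) or all AEs (SAP 6.1). There is no ocular restriction.
2. *Population for non-ocular AEs.* Subjects with at least one treated eye (Protocol 15.7, SAP 6.3).
3. *Planned output.* Each kind of event after surgery is traced through SAP 6.3.1:

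| Treatment-emergent event | Summary table by arm | Listing |
|---|---|---|
| Ocular, non-serious | Ocular AEs | Yes |
| Ocular, serious | Ocular AEs and ocular SAEs | Yes |
| Non-ocular, judged related | ADEs (and SADEs if serious) on one reading; none on the other | Yes |
| Non-ocular, judged unrelated, non-serious | None | Yes |
| Non-ocular, judged unrelated, serious | None | Yes, and the deaths listing if fatal |

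4. *Tally.* Four AE summary tables are planned. None covers all TEAEs, and none covers all treatment-emergent SAEs. The last two rows have no table under any reading.

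5. *Could Protocol 15.7 supply the missing table?* Read alone, "Only treatment emergent adverse events (TEAEs) will be summarized" might seem to promise a summary of every TEAE. The next sentence specifies only the ocular summary, the SAP table list contains no other, and the amendment rationale confirms the intent.

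6. *What the listing contains.* The non-ocular listing in SAP 6.3.1 covers all enrolled subjects and includes events between consent and surgery. The sample size sections plan about 450 enrolled and about 400 treated, so some 450 − 400 = 50 listed subjects would lie outside the subject-level safety set. To obtain the endpoint from the listing, a reader must remove those subjects, remove pre-surgery events, and count by hand against a denominator taken from elsewhere.

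7. *The ADE and SADE tables.* The glossary defines an ADE by its relation to use of the test or control article, with no ocular limit, which favours including related non-ocular events. The tables are nevertheless specified over eyes, and a systemic event has no eye. The text does not settle the matter.

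**The case against.** The strongest reply is that this is a considered reporting choice. Both procedures act locally on the cornea, both lasers are commercially available, and no inferential safety testing is planned. Listing background illness instead of tabulating it is defensible, and Amendment 1 shows that it was intended. That stands as an account of intent. It does not close the gap, because the same amendment revised this endpoint to say treatment-emergent and added no ocular limit.

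A second reply is that nothing is hidden. Non-ocular AEs and deaths are listed, and Protocol 15.7 displays all AE information by treatment and subject. This also stands: a handful of serious events could be counted by hand. What is absent is a prespecified count and percentage by arm.

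A reader might go further and infer that no non-ocular SAE, or no related non-ocular event, is ever counted by arm. The documents do not support that. The ADE and SADE tables omit the word ocular, they carry subject counts, and SAP 3 and 6.3 allow subject-level versions of the set, so related non-ocular events may well be counted there. Nor is the safety objective defeated: ocular TEAEs and SAEs, ADEs, SADEs, surgical problems and device deficiencies are all summarised.

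**Conclusion.** The point holds in a limited form. The endpoint is wider than its analysis. Unrelated non-ocular TEAEs and SAEs have no planned count by arm, and the place of related non-ocular events is ambiguous. This rests only on the current wording of the two documents; the amendment log is used for intent and not as conflicting text.

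No magnitude is claimed, because the documents give no non-ocular event rate. A reader might argue that the missing counts would show or exclude an imbalance between arms. Under an assumed rate of 5% to 20%, 20 to 80 of 400 treated subjects would have such an event. With 200 per arm, the standard error of the difference, √(2p(1−p)/200), is 2.2 to 4.0 percentage points, and the 95% half-width (1.96 × SE) is about 4.3 to 7.8 points. At the lower rate the half-width nearly equals the rate itself, so a moderate imbalance could be neither shown nor excluded. The case is therefore one of consistency and complete reporting. It does not touch the effectiveness conclusions, and it merits correction because the correction is cheap.

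**What to change.** In SAP 6.3.1 and Protocol 15.7:

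- Add a table of all TEAEs, ocular and non-ocular, by SOC and PT.
- Add a table of all treatment-emergent SAEs.
- Base both on the subject-level safety set already named for non-ocular AEs, with subject and event counts by arm.
- State that the ADE and SADE tables include related non-ocular events.

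If an ocular-only endpoint is intended, rename it as ocular TEAEs in Protocol 8.5.2, the synopsis and SAP 6.1, and still keep the all-SAE table.

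The cost is a wording change and one or two tables from data already collected and MedDRA-coded. The drawback is slightly longer output that includes unrelated intercurrent illness.
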